2.5 Rationale for choice of secondary endpoints

It may be difficult to measure success with an antiangiogenic agent using classical measures, such as RECIST, or progression free survival, due to the relative indolent rate of growth of some VHL related lesions. For that reason, we will request, where possible and available, that individuals who enroll on the study furnish imaging studies of their target VHL lesions up to 15 years prior to study enrollment. These studies will be used to generate a growth rate curve of target lesions, onto which the imaging studies acquired during the course of the study will be added. These data will provide information on the relative growth rates of VHL lesions, as well as how this growth rate is influenced by the chronic use of antiangiogenic therapy.

In a similar manner, we will acquire information on prior interventions performed on VHL related lesions in individuals treated on this study. We will calculate the rate of intervention over time, and determine whether this rate changes over the time period the patient is being followed.

2.6 Rationale for choice of preclinical endpoints

Data on circulating cytokine and angiogenic factors suggest these factors provide important prognostic and potential predictive information in patients with RCC. Little is known about how these factors vary as a function of lesion type in VHL at baseline, and whether they predict for benefit from pazopanib therapy. We will collect circulating cells, plasma and sera from patients at baseline, after 12 weeks, 24 weeks and at time of study discontinuation.

It is not known whether specific VHL mutations are associated with response to pazopanib in VHL patients. We will perform exploratory analyses of the relationship between VHL genotype and response to therapy, both globally and according to specific lesion.

## **3.0 PATIENT SELECTION**

- 3.1 Inclusion Criteria
  - 1. Subjects must provide written informed consent prior to performance of study-specific procedures or assessments, and must be willing to comply with treatment and follow-up. Procedures conducted as part of the subject's routine clinical management (e.g., blood count, imaging study) and obtained prior to signing of informed consent may be utilized for screening or baseline purposes provided these procedures are conducted as specified in the protocol.
  - 2. Eastern Cooperative Oncology Group (ECOG) performance status of  $\leq 2$ .
  - 3. Genetically confirmed diagnosis of VHL or measurable disease consistent with the clinical diagnosis of VHL. (Please refer to criterion #5)

Protocol 2011-0465 ASeptember 6, 2017 Page 14 of 50

- 4. Measurable disease criteria:
  - At least one measurable VHL related lesion, which is undergoing surveillance, and patient is not at immediate risk of needing intervention for this or other lesions. Biopsy is not required given the known likely etiology and natural history in the setting of a positive genetic test.
    - a. Brain: asymptomatic hemangioblastoma,  $\geq 0.5$  cm
    - b. Spine: asymptomatic hemangioblastoma,  $\geq 0.5$  cm
    - c. Renal: solid mass suspicious for RCC ≥1 cm or cystic mass (Bosniak 3-4) ≥1 cm.
    - d. Pancreas: solid mass  $\geq 1$  cm and  $\leq 3$  cm suspicious for neuroendocrine tumor, or neuroendocrine tumor > 3 cm but not considered operable.
    - e. Eye: asymptomatic peripapillary and/or macular hemangioblastoma, any size
    - f. Adrenal: asymptomatic or controlled pheochromocytoma greater than 1cm in size
- 5. Patients may have received prior VHL-related systemic therapy, provided not within 14 days or five half-lives of a drug (whichever is longer) prior to the first dose of pazopanib.

Protocol 2011-0465 ASeptember 6, 2017 Page 15 of 50

6. Adequate organ-system function as defined in Table 4.

System	Laboratory Values
Hematologic	
Absolute neutrophil count	$\geq 1.5 \text{ X } 10^{9}/\text{L}$
(ANC)	
Hemoglobin a	$\geq 9 \text{ g/dL} (5.6 \text{ mmol/L})$
Platelets	≥100 X 10  /L
Prothrombin time (PT) or	≤1.2 X ULN
international normalized ratio (INR) b	
Activated partial thromboplastin	≤1.2 X ULN
time (aPTT)	
Hepatic	
Total bilirubin	≤1.5 X ULN
Alanine amino transferase	≤2.0 X ULN
(ALT) and Aspartate	
aminotransferase (AST) c	
Renal	
Serum creatinine	$\leq 2.0 \text{ mg/dL} (133 \mu \text{mol/L})$
Or, if >2.0 mg/dL: Calculated	≥50 mL/min
creatinine clearance (Cl CR )	
(appropriate appendix)	
Urine Protein to Creatinine Ratio	<1
(UPC; appropriate appendix) d	

a. Subjects may not have had a transfusion within 7 days of screening assessment.

b. Subjects receiving anticoagulant therapy are eligible if their INR is stable and within the recommended range for the desired level of anticoagulation or if they are on low molecular weight heparin.

- c. Concomitant elevations in bilirubin and AST/ALT above 1.0 x ULN (upper limit of normal) are not permitted.
- d. If UPC ≥1, then a 24-hour urine protein must be assessed. Subjects must have a 24-hour urine protein value <1 g to be eligible.
- 7. A female is eligible to enter and participate in this study if she is of: Non-childbearing potential including
  - a) any female who has had a surgical procedure rendering her incapable of becoming pregnant.
  - b) Subjects not using hormone replacement therapy (HRT) must have experienced total cessation of menses for  $\geq 1$  year and be greater than 45 years in age, OR, in questionable cases, have a follicle stimulating hormone (FSH) value >40 mIU/mL and an estradiol value < 40 pg/mL (<140 pmol/L).
  - c) Subjects using HRT must have experienced total cessation of menses for  $\geq 1$  year and

Protocol 2011-0465 ASeptember 6, 2017 Page 16 of 50

be greater than 45 years of age OR have had documented evidence of menopause based on FSH and estradiol concentrations prior to initiation of HRT

Childbearing potential, including any female who has had a negative serum pregnancy test within 2 weeks prior to the first dose of study treatment, preferably as close to the first dose as possible, and agrees to use adequate contraception. Novartis Pharmaceuticals acceptable contraceptive methods, when used consistently and in accordance with both the product label and the instructions of the physician, are as follow:

- Complete abstinence from sexual intercourse for 14 days before exposure to investigational product, through the dosing period, and for at least 21 days after the last dose of investigational product.
- Oral contraceptive
- Injectable progestogen.
- Implants of levonorgestrel.
- Estrogenic vaginal ring
- Percutaneous contraceptive patches
- Intrauterine device (IUD)
- Male partner sterilization
- Double barrier method: condom and an occlusive cap (diaphragm or cervical/vault caps) with a vaginal spermicidal agent (foam/gel/film/cream/suppository).

Female subjects who are lactating should discontinue nursing prior to the first dose of study drug and should refrain from nursing throughout the treatment period and for 14 days following the last dose of study drug.

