- 7.2.1 On-study evaluations will consist of the following study activities. A cycle is considered a 4 week period of treatment. Labs that are not drawn at the time of a visit or restaging can be obtained at a medical facility or laboratory that is not directly associated with the Investigator's institution, and forwarded to the Investigator within 96 hours (4 days).
  - Liver Function Test (Serum total bilirubin, SGOT[AST], SGPT [ALT]), will be drawn every two weeks for the first eight weeks (+/- 3 days), and then at the beginning of every cycle (+/- 3 days).
  - Serum chemistry and electrolytes including albumin, alkaline phosphatase, BUN, calcium, creatinine, glucose, LDH, phosphorus, total protein, sodium, potassium, carbon dioxide, chloride, lipase, are to be done at the beginning of every cycle (4 weeks +/- 3 days). Hematology including CBC with differential and platelet counts at the beginning of every cycle (4 weeks +/- 3 days).

• Interim medical history and physical examination (including vital signs and weight) every 12 weeks (+/- 7 days), at the time of restaging (physical examination will only be repeated at C1D1 if > 7 days since screening).

• ECOG performance status with each Physical Exam.

• Record concomitant medications at the time of interim medical history and physical exam (which will be done every 12 weeks +/- 7days). Monitor for adverse events.

Protocol 2011-0465 ASeptember 6, 2017 Page 35 of 50

• Repeat radiographic examination (CT, MRI, as indicated) to evaluate disease progression or response will be done at the end of cycles 3 and 6, and will coincide with interim medical history and physical examination, and every 12 weeks thereafter (if patient continues on treatment) (+/- 7days).

• Retinal examination for those with known retinal lesions at the end of cycles 3 and 6 +/- 7 days.

• Optional blood for correlative studies will be drawn while receiving study drug after 12 weeks +/- 1 week and after 24 weeks +/- 1 week to coincide with the restaging visits.

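### The creatinine entry limit in Table 4 is printed as two values that are not equal: 2.0 mg/dL is 177 µmol/L, and the bracketed 133 µmol/L is 1.5 mg/dL

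*Combined protocol and SAP*

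**What the plan says.** Inclusion criterion 6 in Section 3.1 requires "Adequate organ-system function as defined in Table 4". In the renal part of that table the serum creatinine limit is "\leq 2.0 \text{ mg/dL} (133 \mu \text{mol/L" (the symbols are typesetting markup). One upper limit is given in mg/dL, with a value in µmol/L in brackets after it.

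The next row gives an alternative route to eligibility, introduced by "Or, if >2.0 mg/dL: Calculated" and requiring a creatinine clearance of at least 50 mL/min. This trigger is stated in mg/dL only.

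The hemoglobin row of the same table uses the same two-unit layout: "\geq 9 \text{ g/dL} (5.6 \text{ mmol/L". No other part of the protocol restates the creatinine limit.

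**The concern.** A bracketed value in a second unit is read as the same limit expressed differently. Here the two values are different limits, so one of them is wrong, and the protocol does not say which.

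Take a patient with creatinine of 1.75 mg/dL. On the mg/dL figure the patient is eligible with no clearance check. On the SI figure the patient is over the limit and, read literally, cannot use the clearance route either, because that route starts only above 2.0 mg/dL. Two people checking the same record could reach opposite conclusions about whether an eligibility deviation occurred.

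Reduced renal function is foreseeable in part of this population. A renal mass is one of the qualifying lesions in Section 3.1, item 4, and Section 2.1 reports that 88% of VHL patients with renal cell carcinoma needed intervention.

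**Working it through.** **Inputs**
- From Table 4: limit 2.0 mg/dL; bracketed value 133 µmol/L; clearance trigger above 2.0 mg/dL; clearance limit 50 mL/min; hemoglobin limit 9 g/dL with 5.6 mmol/L in brackets.
- Not in the protocol: the molar mass of creatinine, a chemical constant (C4H7N3O, 113.12 g/mol).

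**Conversion factor.** µmol/L = mg/dL × 10,000 / molar mass, so the factor is 10,000 / 113.12 = 88.40.

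**Attempt to reproduce the printed figure**
- 2.0 × 88.40 = 176.8 µmol/L. The printed value is 133, so it is not reproduced.
- In reverse, 133 / 88.40 = 1.504 mg/dL.
- 1.5 × 88.40 = 132.6, which rounds to 133. The bracketed value is thus the rounded equivalent of 1.5 mg/dL.

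**Sensitivity to the factor**

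| Factor | 2.0 mg/dL in µmol/L | 133 µmol/L in mg/dL |
|---|---|---|
| 88.0 | 176.0 | 1.511 |
| 88.4 | 176.8 | 1.505 |
| 88.5 | 177.0 | 1.503 |

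No plausible factor or rounding closes the gap.

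**Size of the gap**
- 176.8 / 133 = 1.329, so the mg/dL limit is 33% above the SI limit.
- 133 / 176.8 = 0.752, so the SI limit is 25% below the mg/dL limit.
- The band in dispute is above 1.5 and up to 2.0 mg/dL, or 133 to 177 µmol/L.

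**Is the bracket meant as an equivalent?** Hemoglobin serves as a control. Taking 16,114 g/mol for the hemoglobin monomer (also an outside constant), 9 g/dL × 10 / 16,114 × 1,000 = 5.59 mmol/L, which matches the printed 5.6. In that row the bracket is a correct conversion of the lead value, so a reader will take the creatinine bracket the same way.

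**Could the choice of limit matter to a patient?** The protocol's clearance formula is in an appendix that is not available here, so this step assumes Cockcroft-Gault: (140 − age) × weight in kg / (72 × creatinine in mg/dL), multiplied by 0.85 for women. All three examples have creatinine of 1.75 mg/dL (1.75 × 88.40 = 155 µmol/L).
- Woman, 45 years, 60 kg: 95 × 60 × 0.85 / (72 × 1.75) = 4,845 / 126 = 38 mL/min.
- Man, 45 years, 60 kg: 95 × 60 / 126 = 45 mL/min.
- Man, 45 years, 75 kg: 95 × 75 / 126 = 57 mL/min.

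The band therefore holds patients on both sides of the 50 mL/min standard that the table applies above 2.0 mg/dL. The mg/dL figure admits all three without a check.

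**The case against.** The strongest reply is that the table itself shows which figure operates. The 2.0 mg/dL value appears twice, as the lead value and as the clearance trigger, and those two rows fit together with no gap. If 133 µmol/L governed, patients between 1.5 and 2.0 mg/dL would be over the limit with no clearance route, which makes little sense. Most readers would take the bracket as a bad conversion and apply 2.0 mg/dL.

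Exposure also looks small. The protocol reads as run largely from one US cancer centre, which may never use the SI figure. The allowance in Section 7.2.1 that laboratory tests "can be obtained at a medical facility or laboratory that is not directly associated with the Investigator's institution" concerns on-study tests rather than screening. Renal cell carcinoma is not required for entry (Section 2.4), so renal impairment concerns only some of the patients. Creatinine is measured every cycle, Section 6 has no dose rule tied to it, and exclusion criterion 11 lets the investigator keep out patients with serious or unstable conditions.

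Finally, if the clearance alternative is read as open to anyone above either figure, the outcome changes only for patients with clearance below 50 mL/min.

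These points stand as limits on the consequence. They do not make the printed equivalence true. An inference that mg/dL governs also does not show that 2.0 mg/dL was the limit clinically intended: 133 is exactly what a limit of 1.5 mg/dL would carry in brackets.

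**Conclusion.** The concern holds. Table 4 states two limits that differ by 33% relative to the SI value, or 25% relative to the mg/dL value, and presents them as one. Eligibility is in conflict for creatinine above 1.5 and up to 2.0 mg/dL. The only outside input to this conclusion is the creatinine conversion factor, and the result is the same from 88.0 to 88.5. The clearance examples rest further on an assumed Cockcroft-Gault formula and serve as illustration only.

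The protocol does not show which value was intended or how many patients would fall in the band. The sample size, stopping rules and error rates are untouched. It should be corrected because it is an operative entry threshold, but it is not a threat to the trial's inference.

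**What to change.** The sponsor's clinicians choose the intended limit, and Table 4 is then made consistent in one of two ways:
- **If 2.0 mg/dL was meant:** change the bracket to 177 µmol/L. The clearance row already agrees and stays as it is. One entry changes.
- **If 1.5 mg/dL was meant:** print 1.5 mg/dL (133 µmol/L) and change the clearance trigger to above 1.5 mg/dL. Two entries change.

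In either case, adding the µmol/L value to the clearance trigger would keep the two rows aligned in both units. The cost is a minor edit to one table. The second option also tightens entry, because patients between 1.5 and 2.0 mg/dL would then need a clearance of at least 50 mL/min.

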#### 3.2 Exclusion Criteria

- 1. Prior malignancy. Subjects who have had another non VHL related malignancy and have been disease-free for 2 years, or subjects with a history of completely resected non-melanomatous skin carcinoma or successfully treated in situ carcinoma are eligible.
- 2. Clinically significant gastrointestinal abnormalities that may increase the risk for gastrointestinal bleeding including, but not limited to:
  - Active peptic ulcer disease
  - Known intraluminal metastatic lesion/s with risk of bleeding
  - Inflammatory bowel disease (e.g. ulcerative colitis, Chrohn's disease), or other gastrointestinal conditions with increased risk of perforation

Protocol 2011-0465 ASeptember 6, 2017 Page 17 of 50

- History of abdominal fistula, gastrointestinal perforation, or intra-abdominal abscess within 28 days prior to beginning study treatment.
- 3. Clinically significant gastrointestinal abnormalities that may affect absorption of investigational product including, but not limited to:
  - Malabsorption syndrome
  - Major resection of the stomach or small bowel.
- 4. Presence of uncontrolled infection.
- 5. Corrected QT interval (QTc) > 480 msecs using Bazett's formula
- 6. History of any one or more of the following cardiovascular conditions within the past 6 months:
  - Cardiac angioplasty or stenting
  - Myocardial infarction
  - Unstable angina
  - Coronary artery bypass graft surgery
  - Symptomatic peripheral vascular disease
  - Class III or IV congestive heart failure, as defined by the New York Heart Association (NYHA)
- Poorly controlled hypertension [defined as systolic blood pressure (SBP) of ≥ 140 mmHg or diastolic blood pressure (DBP) of ≥ 90mmHg].
   Note: Initiation or adjustment of antihypertensive medication(s) is permitted prior to

study entry. BP must be re-assessed on two occasions that are separated by a minimum of 1 hour; on each of these occasions, the mean (of 3 readings) SBP / DBP values from each BP assessment must be <140/90 mmHg in order for a subject to be eligible for the study

- 8. History of cerebrovascular accident including transient ischemic attack (TIA), pulmonary embolism or untreated deep venous thrombosis (DVT) within the past 6 months. *Note: Subjects with recent DVT who have been treated with therapeutic anti-coagulating agents for at least 6 weeks are eligible*
- 9. Prior major surgery or trauma within 28 days prior to first dose of study drug and/or presence of any non-healing wound, fracture, or ulcer (procedures such as catheter placement not considered to be major).
- 10. Evidence of active bleeding or bleeding diathesis.
- 11. Any serious and/or unstable pre-existing medical, psychiatric, or other condition that could interfere with subject's safety, provision of informed consent, or compliance to study procedures.

Protocol 2011-0465 ASeptember 6, 2017 Page 18 of 50

- 12. Unable or unwilling to discontinue use of prohibited medications list in Section 4.0 for at least 14 days or five half-lives of a drug (whichever is longer) prior to the first dose of study drug and for the duration of the study (Section 5.0).
- 13. Treatment with any of the following anti-cancer therapies:
  - 1. radiation therapy, surgery or tumor embolization within 14 days prior to the first dose of pazopanib OR
  - 2. chemotherapy, immunotherapy, biologic therapy, investigational therapy or hormonal therapy within 14 days or five half-lives of a drug (whichever is longer) prior to the first dose of pazopanib
- 14. Any ongoing toxicity from prior investigational therapy that is >Grade 1 and/or that is progressing in severity, except alopecia.
- 3.3 Inclusion of Women and Minorities

Both men and women and members of all races and ethnic groups are eligible for this trial.

## 4.0 STUDY DRUG

- 4.1 Preparation and Dispensing Pazopanib will be dispensed as capsules at the beginning of each treatment cycle. In case of dose modification, patients will be requested to return all of their previously dispensed capsules.
- 4.2 Concomitant Medications and Non-Drug Therapies If future changes are made to the list of permitted/prohibited medications, formal documentation will be provided by Novartis Pharmaceuticals and stored in the study file. Any such changes will be communicated to the investigative sites in the form of a letter.
- 4.2.1 Permitted Medications

All subjects will be asked to provide a complete list of prescription and over-the-counter medications that have been taken within the 4 weeks prior to Screening. The investigator, or designee, must be informed as soon as possible about any new medication(s) taken from the time of Screening until the completion of the post-treatment follow-up visit.

All concomitant medications taken during the study will be recorded in the GURU database, dose information, and dates of administration.

Subjects should receive full supportive care during the study, including transfusion of blood

Protocol 2011-0465 ASeptember 6, 2017 Page 19 of 50

and blood products, and treatment with antibiotics, analgesics, erythropoietin, or bisphosphonates, when appropriate.

Anti-emetics (such as prochlorperazine, lorazepam, ondansetron or other 5-HT antagonists) may be administered prophylactically in the event of nausea. Caution should be exercised when using 5HT3 drugs in a first-line setting due to the potential for QTC prolongation.

Anti-diarrheals, such as loperamide, may be administered as needed in the event of diarrhea. Although acetaminophen at doses of  $\leq 2$  g/day is permitted, it should be used with caution in subjects with impaired liver function.

#### 4.2.2 Permitted Medications – Use with Caution

#### Specific recommendations regarding anticoagulants:

Results from drug-drug interaction studies conducted in subjects with cancer suggest that pazopanib has no effect on the metabolism of S-warfarin. Hemorrhagic events, however, have been reported in clinical studies with pazopanib; therefore, pazopanib should be used with caution in subjects with increased risk of severe bleeding or who are receiving concomitant anticoagulant therapy (e.g., warfarin or its derivatives, low molecular weight heparin, unfractionated heparin). Subjects taking concomitant anticoagulant therapy should be monitored regularly for changes in relevant coagulation parameters as clinically indicated, as well as for any clinical bleeding episodes.

#### Specific recommendations regarding hypoglycemic therapy including insulin:

Results from drug-drug interaction studies conducted in subjects with cancer suggest that there will be no clinically relevant pharmacokinetic interaction between pazopanib and hypoglycemic agents. Transient decreases in serum glucose (mainly Grade 1 and 2, rarely Grade 3) have been observed in clinical studies with pazopanib. In addition, decreases in blood sugar have been recently reported in subjects treated with another small molecule

tyrosine kinase inhibitor, sunitinib. Such changes may require an adjustment in the dose of hypoglycemic and/or insulin therapy. Subjects should be advised to report symptoms of hypoglycemia (e.g., confusion, visual disturbances, palpitations, sweating). Serum glucose should be tested during treatment with pazopanib as outlined in the protocol and as clinically indicated.

#### Specific recommendations regarding agents that prolong QT interval:

Pazopanib should be used with caution in patients with a history of QT interval prolongation, in patients taking antiarrhythmics or other medications that may prolong QT interval, and those with relevant pre-existing cardiac disease.

#### The Effects of Pazopanib on Other Drugs

*In vitro* data indicate that pazopanib is a potential inhibitor for CYP3A4, CYP2C8, CYP2D6, CYP1A2, CYP2C9, CYP2C19, CYP2A6, CYP2B6, and CYP2E1. Pregnane X receptor

Protocol 2011-0465 ASeptember 6, 2017 Page 20 of 50

transient transfection assay suggested some potential for human CYP3A4 induction at high concentrations. Results from drug-drug interaction studies conducted in subjects with cancer suggest that pazopanib is a weak inhibitor of CYP3A4, CYP2C8, and CYP2D6 *in vivo*, but had no clinically relevant effect on CYP1A2, CYP2C9 or CYP2C19 metabolism. Therefore, concomitant use of pazopanib with certain medications (substrates of CYP3A4, CYP2C8, and CYP2D6) with a narrow therapeutic window should be undertaken with **CAUTION** due to the potential for alterations in the pharmacologic effects of these medications or an increased risk for serious or life threatening adverse events associated with such medications (see below) secondary to the inhibition of specific CYP enzymes by pazopanib. In addition, the potential for drug interaction with such medications, although diminished, may persist after the last dose of pazopanib due to its long half-life (i.e., mean 30.9 hours); therefore, continue to exercise **CAUTION** for at least 7 days and up to 15 days after the last dose of pazopanib when administering these medications. These medications include (but are not limited to):

- Ergot derivatives: dihydroergotamine, ergonovine, ergotamine, methylergonovine (potential increased risk for developing ergot toxicity that includes severe vasospasm leading to perpazopanibheral as well as cerebral ischemia)
- Neuroleptics: pimozide (potential increased risk for QT interval prolongation, ventricular arrhythmia, and sudden death)
- Antiarrhythmics: bepridil, flecainide, lidocaine, mexiletine, amiodarone, quinidine, propafenone (potential increased risk for QT interval prolongation and Torsade de Pointes)
- Immune modulators: cyclosporine, tacrolimus, sirolimus (potential increased risk for nephrotoxicity and neurotoxicity)
- Miscellaneous: quetiapine, risperidone, clozapine, atomoxetine.
- 4.2.3 The Effects of Other Drugs on Pazopanib
  - Results from *in vitro* studies suggest that the oxidative metabolism of pazopanib in human liver microsomes is mediated primarily by CYP3A4, with minor contributions from CYP1A2 and CYP2C8. Furthermore, *in vitro* data suggest that pazopanib is a substrate for p-glycoprotein. Substances that induce or inhibit CYP3A4 may alter the pharmacologic effects of pazopanib and should be used with CAUTION. Medications that inhibit CYP3A4 may result in increased plasma pazopanib concentrations. Selection of an alternate concomitant medication with no or minimal potential to inhibit CYP3A4 is recommended. A dose reduction to 400 mg pazopanib should be considered when it must be co-administered with strong CYP3A4 inhibitors. Strong CYP3A4 inhibitors include (but are not limited to):
    - Antibiotics: clarithromycin, telithromycin, troleandomycin
    - HIV: protease inhibitors (ritonavir, indinavir, saquinavir, nelfinavir, amprenavir, lopinavir)
    - Antifungals: itraconzaole, ketoconazole, voriconazole, fluconazole

Protocol 2011-0465 ASeptember 6, 2017 Page 21 of 50

- Antidepressants: nefazodone CYP3A4 inducers may decrease plasma pazopanib concentrations. Selection of an alternate concomitant medication with no or minimal enzyme induction potential is recommended.
- Grapefruit juice should be avoided as it inhibits CYP3A4 activity and may also increase plasma concentrations of pazopanib.
   Drugs that induce CYP3A4 and may decrease pazopanib plasma concentrations include (but are not limited to):
- Glucocorticoids: cortisone (>50 mg), hydrocortisone (>40 mg), prednisone (>10 mg), methylprednisolone (>8 mg), dexamethasone (>1.5 mg)
- Anticonvulsants: phenytoin, carbamezepine, phenobarbital, oxcarbazepine
- HIV antivirals: efavirenz, nevirapine
- Antibiotics: rifampin (rifampicin), rifabutin, rifapentene
- Miscellaneous: St. John's Wort, modafinil, pioglitazone, troglitazone

